Prevalence of obstructive sleep apnoea among adolescents in the general population

Study protocol

Abstract

Obstructive sleep apnoea (OSA) is associated with a variety of important complications, namely cardiovascular, neurocognitive and metabolic disturbances. The prevalence of OSA is well studied in children and adults. However, adolescence – an interface between childhood and adulthood, and a period of developmental changes known to affect sleep is largely unexplored in relation to OSA. The only published prevalence study on adolescents is limited by its small sample size, not a true representation of the general population and primarily focused on Caucasians. In this proposed study, we aim to determine the prevalence of OSA and associated clinical features in a large population-based sample of adolescents aged between 12 and 16 years.

The sample selection will be based on a stratified (by districts) and clustered (subjects within randomly selected schools) randomised sampling frame. We will stratify all secondary schools registered under the Education Bureau according to the four geographic regions in Hong Kong. In order to avoid sampling bias towards the region that has less population, the final number of schools to be recruited from each of the 4 geographical regions will be in proportion to the adolescent population that resides in that region. Students in each year grade from the chosen school will be randomly selected and invited to take part. Each participant will fill in a sleep habit questionnaire, undergo anthropometric measurements, complete polysomnographic recordings at home and will also have phenotyping for cardiovascular and metabolic risk. The primary outcome is prevalence of OSA, assessed by the obstructive apnoea hypopnoea index. Secondary outcomes include use of logistic regression models to assess association between different severities of OSA and various demographic and clinical variables, and risk of diabetes, hypertension and metabolic syndrome.

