Adolescence is a rapid and critical transitional stage of physical and psychological development that generally occurs at the onset of puberty. Major biological changes take place during this period and they include changes to the sex organs, physical parameters, muscle mass, as well as vital developmental changes in brain structure and organization. It is well known that some of these changes will affect various aspects of sleep, predisposing adolescents to the development of OSA. [2-4] This period of growth and maturation is very distinct and should not be seen as a continuum of childhood, and it further emphasizes the importance not to extrapolate childhood OSA information to adolescents.

Research by our research group

We have successfully conducted clinical research on various aspects of childhood OSA. These include determining risk factors and prevalence, [1] establishment of screening methods, [18] examination of neurocognitive, metabolic and cardiovascular complications using cross-sectional and longitudinal study design. [19-27] Our group has also published work on the natural progression of mild OSA and primary snoring in children. [28,29] We have also recently completed a 10-year follow-up study on an OSA cohort and we document that moderate-to-severe OSA in childhood may be associated with higher blood pressure in early adulthood. [30] Thus our proposed study builds on our established track record in childhood OSA research.

(b) Research plan and methodology

Study Subjects

Adolescents will be recruited from local secondary schools which will be randomly selected from the 4 geographic regions of Hong Kong. Inclusion and exclusion criteria are as follows:

Inclusion criteria:

1. adolescents aged 12-16 years.
2. written informed consent from parents and assent from participants available.

Exclusion criteria:

1. subjects who have previously undergone upper airway surgery or currently receiving treatment for OSA.
2. craniofacial anomalies.
3. subjects who are unable to speak or read Chinese.

The study protocol will be submitted to ethic committee of the New Territory East Cluster Board for approval. All subjects will participate on a voluntary basis. The study will be conducted in compliance with the Declaration of Helsinki.

Study Design

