It is a cross-sectional, population-based study. Subjects who are found to meet all the inclusion and none of the exclusion criteria will be recruited. They will complete a set of sleep-related questionnaires, undergo anthropometric measurements, home polysomnographic (PSG) monitoring, attention assessment and phenotyping of their metabolic and cardiovascular risk.

Pilot Data and Sample Size Estimation

We have previously established a school-based cohort in 2003-2005 which included children aged between 6 and 13 years to determine the prevalence of OSA. [1] We then conducted a 4-year follow-up for a subgroup of the cohort was carried out. [25] At follow-up, the subjects were aged between 10 and 17 years. A total of 243 teenagers returned for the follow-up visit. The prevalence of OSA defined by different cut-offs and the minimum sample size required to detect corresponding prevalence with various levels of precision are presented in table 1. On further analysis those who returned for the 4-year follow-up had higher baseline OSA severity compared to the rest of the cohort [OAHl: 1.0 (0.1–2.5) c.f. 0.6 (0–2.0), $p=0.007$], therefore the calculated prevalence is likely an over-estimation. Nonetheless, using the proposed sample size would provide adequate power should the genuine population prevalence is lower than the calculated one.

Table 1. Minimum sample size required to detect the prevalence of OSA defined by various cut-offs with different levels of precision.

	OAHl $\geq 5/h$	OAHl $\geq 1/h$	OAHl $\geq 1/h$ + habitual snoring (ICSD criteria)
No. of cases	34/243	120/243	31/243
Prevalence	0.140	0.494	0.128
Precision			

	Minimum sample size required		
0.01	4623	9603	4276
0.015	2055	4268	1900
0.02	1156	2401	1069
0.025	740	1536	684
0.03	514	1067	475
0.04	289	600	267
0.05	185	384	171

In the current settings with limited budget allocation, our research team is capable of recruiting 740 adolescents to detect a prevalence of 14.0% with a precision of 2.5% (i.e. 95%CI: 11.5–16.5%) for the OAH1 \geq 5/h cutoff. The sample size can also ensure a precision of <4% for the OAH1 \geq 1/h cut-off and a precision of <2.5% for the ICSD criteria. [31] The sample size would also provide >99% power to detect the differences between the estimated prevalence of OSA in adolescents and the published prevalence of OSA in primary school children [1] no matter which cut-off is being used.

Sampling Frame

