The sample selection will be based on a stratified (by districts) and clustered (subjects within randomly selected schools) randomised sampling frame. We stratify all secondary schools registered under the Education Bureau according to the four geographic regions in Hong Kong (i.e. Hong Kong Island, Kowloon, New Territories East and New Territories West). The student numbers in all secondary schools are available in the Bureau's website. Ten students in each school year grade will be randomly selected from the chosen schools. There are on average 50 children to be recruited per schools therefore we will need to randomly select 15 secondary schools from the whole of Hong Kong. In order to avoid sampling bias towards the region that has less population, the final number of schools to be recruited from each of the four geographical regions would be in proportion to the adolescent population that reside in that region. According to the 2016 population by-census statistics (available from the website of Census & Statistics Department, HKSAR), the proportions of adolescents residing in Hong Kong Island, Kowloon, New Territories East and New Territories West were 16.1%, 30.7%, 25.3% and 27.9% respectively. Thus, this study will recruit proportionally 2, 5, 4 and 4 secondary schools from the 4 regions. This sampling method ensures that our subjects are representative of the local school population. Lastly, this study will recruit and survey the subjects from the four regions in parallel throughout the study period in order to minimise the possible influences of different seasons on study outcomes.

Outcome Measures

- (a) Primary outcome: prevalence of obstructive sleep apnoea as defined by obstructive apnoea hypopnoea index.
- (b) Secondary outcomes: correlation between severity of OSA with clinical, laboratory parameters and cognitive function as measured by Conners' Continuous Performance Test (CPT).

Collection of Data

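### School selection makes no stated use of school size; with a fixed ten per grade and region-only weights, representativeness within regions is not ensured as claimed

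*Combined protocol and SAP*

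**What the plan says.** Three places in the combined protocol and SAP describe the draw.

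- Abstract: "Students in each year grade from the chosen school will be randomly selected and invited to take part".
- Study Subjects: "Adolescents will be recruited from local secondary schools which will be randomly selected from the 4 geographic regions of Hong Kong".
- Sampling Frame: "There are on average 50 children to be recruited per schools therefore we will need to randomly select 15 secondary schools", followed by the allocation of 2, 5, 4 and 4 schools to the four regions.

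None of them gives a school's probability of selection. Sampling Frame also says "The student numbers in all secondary schools are available" from the Education Bureau's website, but gives those figures no role in selecting schools or weighting students. Within a school the take is constant: "Ten students in each school year grade will be randomly selected from the chosen schools".

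The regional allocation has a stated purpose: "In order to avoid sampling bias towards the region that has less population". The section then says that this method ensures a sample representative of local school pupils.

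Statistical Analysis computes a prevalence P_i for each region and combines the regions with weights N_i/N. It does not say how P_i is formed from the schools in a region, and it has no school-level or student-level weight.

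**The concern.** The primary outcome is a population prevalence, so the students in the sample should stand in known proportion to the students in the population. The plan guards against distortion between regions, but describes no step against the same distortion between small and large schools inside a region. A fixed take from schools drawn without regard to size gives students in small grades a higher chance of inclusion. If OSA prevalence differs with school size, the regional figures are shifted. The N_i/N weights cannot correct this because they act only between regions, and more students per school would leave it unchanged.

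**Working it through.** **The plan's own figures.** Pilot Data and Sample Size Estimation plans 740 adolescents to "detect a prevalence of 14.0% with a precision of 2.5" percentage points. 1.96² × 0.14 × 0.86 / 0.025² = 740.0, which reproduces. 740/50 = 14.8, hence 15 schools. Multiplying 15 by the regional shares 16.1%, 30.7%, 25.3% and 27.9% gives 2.42, 4.61, 3.80 and 4.19, which round to 2, 5, 4 and 4. None of these figures is in dispute.

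**Inclusion probability within a region.** Let k of K schools be drawn and let a grade have g students.

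- Equal-probability draw: (k/K) × (10/g). A student in a grade twice as large has half the chance.
- Draw proportional to enrolment: (k × school enrolment / regional enrolment) × (10/g). If g is a constant share of school enrolment, school size cancels and all students have the same chance.

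**Size of the bias under the equal-probability reading.** The absolute difference between the equal-weighted and enrolment-weighted means of school prevalences is |r| × CV × SD_P. Here r is the correlation of school prevalence with school size, CV is the coefficient of variation of school size, and SD_P is the between-school standard deviation of prevalence. The 14% is the plan's figure. The intraclass correlation (ICC), CV and r are assumptions, because the documents give none of them.

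SD_P = √(ICC × p × (1 − p)) = √(0.02 × 0.14 × 0.86) = 4.91 points.

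| \|r\| | Bias, CV 0.3 (points) | Bias, CV 0.4 (points) | Share of 2.5 points |
|---|---|---|---|
| 0 | 0 | 0 | 0 |
| 0.1 | 0.15 | 0.20 | 6–8% |
| 0.3 | 0.44 | 0.59 | 18–24% |
| 0.5 | 0.74 | 0.98 | 29–39% |

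At |r| = 0.1, 0.3 and 0.5 the ranges are 0.10–0.14, 0.31–0.42 and 0.52–0.69 points with ICC 0.01, and 0.23–0.31, 0.70–0.93 and 1.16–1.55 points with ICC 0.05. If large schools have the higher prevalence the estimate is too low; if small schools do, it is too high.

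**Illustration at the same CVs.** Take equal numbers of small and large schools. The size ratio is (1 + CV)/(1 − CV) = 1.86 or 2.33. Small schools hold (1 − CV)/2 = 35% or 30% of students but supply 50% of the sample. Each 1-point prevalence gap between the two groups shifts the estimate by CV/2 = 0.15 or 0.20 points.

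**Simulation of the alternatives.** The settings were 2, 5, 4 and 4 schools, the plan's regional weights, 49 students per school, ICC 0.02, CV 0.3 and 0.4, r from −0.5 to 0.5, and 40,000 runs per setting.

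| Design | Bias | Root-mean-square error (points) |
|---|---|---|
| Equal probability, unweighted | up to 0.99 points | 1.79–2.05 |
| Proportional to enrolment | within 0.01 points | 1.79–1.85 |
| Equal probability, inverse-probability weighted | 28–36% of the unweighted bias remains | 1.85–2.01 |

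The weighted analysis raises the standard error by 2–11%. It lowers total error clearly only at r = −0.5.

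**The case against.** The strongest reply is that the enrolment sentence implies size-proportional selection. It stands between the stratification of schools and the draw of students, and the regional allocation uses by-census figures instead, so the enrolment figures have no other stated use there. This stands as a possibility: size-proportional selection is not excluded. A reader might infer that the plan adopts equal-probability selection, but the text does not say that either. It leaves the estimator undetermined, which one sentence would settle.

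Second, no bias is shown. This also stands. The candidate risk factors in Statistical Analysis are all individual characteristics, and nothing in the documents links OSA to school size. The larger figures need |r| = 0.5, for which the documents give no grounds.

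Third, ten per grade need not yield equal analysed numbers. The plan speaks of an average of 50 per school, and "All subjects will participate on a voluntary basis". A pooled P_i is weighted by participants, so calling it a school average is only approximate. That qualifies the description without restoring proportionality to school size.

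Fourth, the sentence about representativeness closes the argument on regional allocation. Read as a claim about regions it is reasonable, but it is worded as a claim about the whole local school population.

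**Conclusion.** The point holds as a gap in the stated design that is cheap to close. The school selection probabilities and the formation of P_i are not given. On the plain reading students in small schools are over-represented within each region, so the assurance of representativeness is unsupported at that level. The bias needs three conditions together: schools drawn with equal probability, schools that differ in size, and prevalence related to size. Without the last it is zero. On the assumed inputs it is small at |r| = 0.1 and stays below 1 point at |r| = 0.5 (ICC 0.02), against a stated 2.5 points.

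A reader might go further and conclude that the prevalence estimate will be biased, or that the 740 or the 2/5/4/4 split is wrong. The documents support neither: they give no evidence on size and prevalence, and both figures reproduce. Changing the plan is worthwhile because the better method is concrete and, in simulation, removed the bias with a root-mean-square error never more than 0.02 points above that of the unweighted design.

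**What to change.** In Sampling Frame, state that schools within each region are selected with probability proportional to enrolment, using the Bureau's student numbers, and that replacements for schools that refuse are drawn from the same region by the same rule. Ten per grade is then approximately self-weighting. Replace the word *ensures* with the selection probabilities. In Statistical Analysis, state that P_i is the pooled proportion in the region.

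This needs no extra schools or students. Its downside is that self-weighting is only approximate, because grade shares, participation and school refusal vary. For grade shares alone, with an assumed CV of 0.1, the residual bias is 0.1 × 0.1 × 4.91 = 0.05 points at a correlation of 0.1, and 0.5 × 0.1 × 4.91 = 0.25 points at 0.5.

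If schools have already been drawn with equal probability, keep the unweighted estimate as primary and state the limitation. An enrolment-weighted estimate can be an optional sensitivity analysis, with weight (schools in region / schools sampled) × (grade enrolment / participants in that grade). It should go no further than that: with 2 to 5 schools per region it leaves about a third of any bias and costs some precision. Grade enrolment also only approximates the eligible individuals that N_i counts, which should be said beside the result.

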The obtained result will provide the much needed OSA prevalence in adolescents which is essential for estimating the true burden of disease within this population. This information is also vital when considering population-based health policies and interventional strategies. Globally, the findings from currently evidence-sparse region of the world allow future international comparison of disease burden. Our study will also form a platform from which repeated measurements can be made to assess time trends and to answer the important question of whether adulthood OSA takes its origin from adolescence.

Hypothesis

We hypothesize that the prevalence of obstructive sleep apnoea among adolescents is different from that reported for children.

Key Issues

(1) Our research group has demonstrated that childhood OSA is common in Hong Kong. We found OSA prevalence for boys and girls aged between 5 and 13 years being 5.8% and 3.8% respectively. [1] However, the prevalence of OSA in adolescents remains unknown. It is inaccurate to extrapolate prevalence of childhood OSA to adolescents as they go through a period of critical transition. In fact adolescence is associated with various developmental changes,

namely somatic growth, cerebral remodeling [2] and hormonal changes that can affect upper airway dynamics [3] and ventilator control. [4] These changes are expected to influence upper airway patency during sleep.

The only published study that examined OSA prevalence among adolescents involved a small sample size of 101 subjects. [5] After completion of an 82-item questionnaire, all participants underwent overnight cardiorespiratory monitoring at home. Twenty-nine percent of the subjects were snorers. Polygraphy showed a respiratory disturbance index ≥ 10 in 18 subjects (17.8%), but concurrent symptoms suggestive of OSA were found in only 2 subjects (1.9%). Further studies with sound methodology and a representative sample of the studied population are required to provide a reliable estimation of OSA in adolescents.

(2) Obstructive sleep apnoea in children and adolescents is an important clinically relevant condition because of its association with a number of significant short and long term consequences. [6] Specifically for adolescents, both metabolic disturbances (dyslipidaemia and insulin resistance) and cardiac complications (hypertension, left ventricular diastolic dysfunction and increased left ventricular mass) are well established OSA sequelae. [7-9]

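### Does a plan for 15 schools of 50 students, against a minimum of 740, leave too little room for refusals and inadequate recordings?

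*Combined protocol and SAP*

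**What the plan says.** Under Pilot Data and Sample Size Estimation, the protocol takes 740 from Table 1, where the figures are labelled as minimum sample sizes: "our research team is capable of recruiting 740 adolescents to detect a prevalence of 14.0% with a precision of 2.5" percent, for the OAHI ≥5/h cut-off. It links this number to a limited budget. It also warns that the 14.0% comes from a follow-up subgroup with higher baseline severity, and "therefore the calculated prevalence is likely an over-estimation".

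Under Sampling Frame, the draw within schools is described as "Ten students in each school year grade will be randomly selected from the chosen schools". The next sentence gives the yield and the number of schools: "There are on average 50 children to be recruited per schools therefore we will need to randomly select 15 secondary schools". The Abstract describes the same step as "Students in each year grade from the chosen school will be randomly selected and invited to take part".

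Under Study Subjects, the second inclusion criterion is "written informed consent from parents and assent from participants available". Under Study Design, "Subjects who are found to meet all the inclusion and none of the exclusion criteria will be recruited".

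The Sleep study section defines an adequate home recording as one with more than 6 hours of sleep. It does not say what happens to a recording that falls short. The Feasibility and Timetable section allots 93 weeks to 740 subjects at 8 per week, and keeps 10 further weeks for school clashes, missed appointments and holidays.

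**The concern.** Two adjacent sentences in Sampling Frame appear to treat ten students selected per grade and 50 recruited per school (five grades of ten) as the same count. Participation is voluntary, needs a parent's consent and the student's assent, and is subject to exclusions. If the 50 are only the students invited, the 10 spare students would have to absorb every refusal, every exclusion and every failed recording. If the 50 are already enrolled, the 10 must still cover all inadequate recordings.

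Several omissions add to the impression. No loss rate or inflation of the sample size is given, and the 93 weeks are sized to 740 assessments. The actigraphy section has an exclusion rule for nights, while the sleep study that determines the primary outcome has a threshold but no stated consequence. At stake would be the stated ±2.5 points. There is also a possible selection effect, if students who slept 6 hours or less were dropped or replaced.

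**Working it through.** **Inputs.** From the protocol: prevalence at OAHI ≥5/h of 34/243 (0.140); ICSD criteria 31/243; OAHI ≥1/h 120/243; precision 0.025; 95% confidence (z = 1.96); 50 per school; 15 schools; 8 assessments per week; 93 + 10 weeks. Assumed, because the documents give no values: the loss rates, the lower prevalences and the intraclass correlation.

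**1. The plan's own figure.** n = z²p(1−p)/d² = 1.96² × (34/243) × (209/243) / 0.025² = 739.7, so 740. This agrees with Table 1. Schools: 740/50 = 14.8, so 15. Students: 15 × 50 = 750. Margin: 10/750 = 1.3%.

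**2. What the 750 are.** Sampling Frame says the 50 are to be recruited. Study Design recruits only those who meet all the inclusion criteria and no exclusion criterion, and consent with assent is one of the inclusion criteria. Read together, a recruited student has consented and is eligible. Refusals and exclusions therefore come before the 750 and do not reduce it. Only inadequate recordings can.

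**3. Precision under assumed loss from 750.** Half-width = 1.96 × √(0.14 × 0.86 / n), ignoring clustering:

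| Assumed loss | n | Half-width (points) |
|---|---|---|
| 0% | 750 | ±2.48 |
| 1.3% | 740 | ±2.50 |
| 5% | 712 | ±2.55 |
| 10% | 675 | ±2.62 |
| 20% | 600 | ±2.78 |
| 30% | 525 | ±2.97 |
| 50% | 375 | ±3.51 |

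**4. The other two precision claims.** The ICSD claim (under 2.5 points) needs 684 in Table 1, so it tolerates a loss of 66/750 = 8.8%. The OAHI ≥1/h claim (under 4 points) needs 600, so it tolerates about 150/750 = 20%.

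**5. If the prevalence is below 14%, as the protocol expects.** Students needed for ±2.5 points:
- at 13%: 695.2, so 696; tolerated loss 54/750 = 7.2%
- at 12%: 649.1, so 650; tolerated loss 100/750 = 13.3%
- at 10%: 553.2, so 554; tolerated loss 196/750 = 26.1%

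**6. The comparison with children.** The hypothesis is "We hypothesize that the prevalence of obstructive sleep apnoea among adolescents is different from that reported for children". Using a one-sample normal test, two-sided 5%, against a fixed 5% (the top of the 3–5% range quoted for children on ICSD-II criteria) and ignoring clustering, power is 99.9% at a prevalence of 0.128 with n = 375, and 98% at an assumed 0.10 with n = 450. Against 5.8%, the figure quoted for boys, the last case gives 93%.

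**7. Calendar room.** The 93 weeks give 93 × 8 = 744 slots. The 10 reserve weeks add 80, for 824 in all. After 750 first nights, 824 − 750 = 74 slots remain, shared with the other stated uses of those weeks. Repeating 5% of recordings (38) would take 788 slots, or 98.5 weeks. Repeating 10% (75) would take 825, one more than the total.

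**8. Clustering for scale.** With 50 per school and an assumed intraclass correlation of 0.005, the design effect is 1 + 49 × 0.005 = 1.245. The half-width at 750 is then 2.48 × √1.245 = ±2.77 points with no loss at all. A 5% loss takes it to about ±2.83.

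**The case for a change.** The strongest case for a change is that reading *recruited* as enrolled does not close every gap. The plan never explains how ten selected students become ten enrolled ones in each grade, and it does not say whether 740 is a number enrolled or a number evaluable. A reserve of 10 is thin for unattended home recordings that must exceed 6 hours of sleep. Without a stated rule, the team would decide case by case whether to repeat, replace or drop a short recording, and two of those choices select against short sleepers. Writing the rules down would cost little.

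Most of this stands as description: the step, the status of 740 and the rule are missing. The harm is not demonstrated. No loss rate appears in the documents, so no stated precision is shown to be missed. No figure links short sleep to the apnoea index, so the selection effect has neither a size nor a direction. The return difference in the earlier cohort shows that participation can relate to severity, but says nothing about the direction in this survey.

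The obvious remedies also gain little. Inviting students from a random list until ten per grade consent produces the same 750. Restating the precision as ±2.55 at 712 would replace one figure that ignores clustering with another. Repeat nights can be fitted into the reserve weeks up to a point without amending anything.

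**Conclusion.** No change to the plan follows. On the protocol's own usage the 750 are consented and eligible students, which covers the 740. Only inadequate recordings can erode that number, and a loss of 5% to 10% (assumed) would cost about 0.05 to 0.12 points of half-width at 14%. If the prevalence is 13% or 12%, the stated ±2.5 points would hold through a loss of about 7% or 13%. The comparison with children is not threatened by this margin: power stays above 90% in every case checked.

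This rests on reading *recruited* consistently across Sampling Frame, Study Design and the inclusion criteria, and on losses of ordinary size. If the 50 were only students invited and half were lost, the half-width would be ±3.51 points: a wider interval, though still a usable estimate.

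What is missing is operational detail that a competent team would supply: inviting further students when some decline, repeating a failed night where the calendar allows, and reporting response and adequate-recording rates. The effect of clustering on precision is a separate matter, and under the small intraclass correlation assumed above it outweighs a loss of this order.

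### Random selection does not by itself make participants representative, and the region-only prevalence estimator has no safeguard against selective participation

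*Combined protocol and SAP*

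**What the plan says.** Sampling Frame draws 15 schools at random within four regions, in proportion to the adolescent population, and ten students at random per grade. It concludes: "This sampling method ensures that our subjects are representative of the local school population".

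Other sections show that selection is only the first step. The Abstract says: "Students in each year grade from the chosen school will be randomly selected and invited to take part". Study Subjects says: "All subjects will participate on a voluntary basis", and lists as an inclusion criterion "written informed consent from parents and assent from participants available". Taking part means questionnaires, body measurements, a home sleep study, an attention test, a week of actigraphy and fasting blood, usually with a visit to the unit.

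Pilot Data and Sample Size Estimation reports that, in the team's earlier school cohort, "those who returned for the 4-year follow-up had higher baseline OSA severity compared to the rest of the cohort" (OAHI 1.0 (0.1–2.5) against 0.6 (0–2.0), p = 0.007). The plan infers that its pilot prevalence is probably too high, but uses this only to argue that the sample size remains adequate.

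Statistical Analysis computes overall prevalence as the sum of region size times region prevalence, divided by total population. No other weight appears. The plan states no expected response rate, replacement rule, comparison of participants with decliners, or sensitivity analysis for non-response.

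**The concern.** The primary outcome is a population prevalence. If the chance of accepting depends on OSA, or on something related to it such as snoring or sex, the prevalence among participants differs from that among eligible students. Weighting by region corrects only for differences between regions. A larger sample does not help: it narrows the interval around the wrong value.

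The word 'ensures' therefore claims a property that the design does not have. The recruitment numbers also leave almost no room for refusal, and the plan does not say what happens when a selected student declines. Replacing decliners with willing students would fill the sample while hiding the selection.

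**Working it through.** **1. The plan's own figure.** Table 1 gives 34/243 = 0.140 at OAHI ≥5/h. Under simple random sampling, n = 1.96² × p(1 − p)/d² with d = 0.025 gives 739.7, so 740. This reproduces the plan. The half-widths at n = 740 are 2.5 points (≥5/h), 3.6 points (≥1/h) and 2.4 points (ICSD).

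**2. Room for refusal.** 15 schools × 50 students = 750. If 750 is the number invited, reaching 740 needs 740/750 = 98.7% participation. The text can also be read as 50 recruited per school, which would require replacements under a rule that is not given.

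**3. Bias as a function of participation.** Let R be the participation probability of students with OSA divided by that of students without. For true prevalence p,

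observed prevalence = pR / (pR + 1 − p).

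R is not in the documents; the values below are assumptions, with true p = 14%. Coverage is for the nominal 95% interval at n = 740 under simple random sampling.

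| R | Observed | Shift (points) | Coverage |
|---|---|---|---|
| 0.8 | 0.112/0.972 = 11.5% | −2.5 | – |
| 1.1 | 0.154/1.014 = 15.2% | +1.2 | about 85% |
| 1.25 | 0.175/1.035 = 16.9% | +2.9 | about 44% |
| 1.5 | 0.210/1.070 = 19.6% | +5.6 | about 3% |

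**4. The ratio that uses up the precision.** Rearranged, R = odds(observed)/odds(true).

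- True 14.0% observed as 16.5%: 0.1976/0.1628 = 1.21.
- True 11.5% observed as 14.0%: 0.1628/0.1299 = 1.25.
- The same calculation gives about 1.16 at ≥1/h and about 1.27 for ICSD.

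**5. What the earlier cohort can say.** I read its figures as median (interquartile range), which is an assumption. If participants and non-participants differed as returners did from the rest, bias = (1 − response rate) × gap in prevalence.

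- At ≥1/h, 50% of returners are cases, against about 39% (lognormal) to 43% (linear interpolation) of the rest. The gap of 7 to 11 points gives a bias above 3.6 points if response is below about 50% to 68%.
- At ≥5/h, the cut-off used for sizing, both upper quartiles (2.5 and 2.0) lie well below the threshold, so the answer depends on the assumed tail. The odds ratio is about 1.0 (lognormal) to 1.42 (exponential). Scaled to 14%, the gap is 0 to 3.7 points. The bias passes 2.5 points only under the exponential tail with response below about 33% (1 − 2.5/3.74).

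**6. What calibration by sex can correct.** Key Issues gives child prevalences of 5.8% (boys) and 3.8% (girls). If the share of boys among participants were off by 10 percentage points (assumed), prevalence would move by 0.10 × 2.0 = 0.2 points. If the same ratio, 5.8/3.8 = 1.53, held around 14% with equal numbers of each sex, the two figures would be about 16.9% and 11.1%, and the shift 0.10 × 5.8 = 0.6 points. Calibration removes this part but not OSA-related selection within sex and grade.

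**The case against.** Several points on the other side stand.

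- **The evidence is indirect.** The cohort finding concerns return to a 4-year follow-up by a subgroup of children whose OAHI had already been measured. The plan does not say whether that subgroup selected itself. A reader might infer that the pilot shows severer cases take part more in a study like this one. The documents do not support that: they say nothing about first participation of randomly invited students.
- **The size is assumed.** A reader might take ratios of 1.5 or 2 as plausible and expect prevalence to be overstated by 5 points or more. At ≥5/h the cohort figures point to an odds ratio of 1.0 to 1.42, so they do not support such ratios well.
- **The direction is open.** The burden of assessment could deter either group. Excluding students with past airway surgery or current OSA treatment lowers the figure relative to all adolescents.
- **The comparison with children is not necessarily distorted.** A reader might infer that self-selection will create a false difference from the child figure. That figure comes from the same team's school-based cohort, so only a difference in bias between the two studies matters, and the documents do not allow it to be estimated.
- **Snoring explains only part at ≥1/h.** In Table 1, 31 of 120 such cases (26%) were habitual snorers. If habitual snorers were twice as likely to join, R would be at most 1 + 0.258 = 1.26, and less once snoring non-cases are counted. That ceiling still exceeds the 1.16 in step 4, and it does not apply to the ICSD definition, which includes snoring.

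If 98.7% of selected students truly took part, non-response at that stage would hardly matter. The plan gives no reason to expect this.

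**Conclusion.** The point holds as a gap in the claim and in the estimator, not as a demonstrated bias. Random invitation does not ensure representative participants, and region weights alone do not address who accepts. A participation ratio of about 1.21 to 1.25 would be enough to match the stated 2.5-point precision at OAHI ≥5/h; 1.1 would cost about 1.2 points; 0.8 would understate a true 14% by about 2.5 points. These results rest on assumed ratios and on the plan's simple-random-sampling half-width. Clustering by school would widen the interval, so a somewhat larger ratio would then be needed to match it. The earlier cohort supports a bias above precision more clearly at ≥1/h than at ≥5/h, and only indirectly at either. This is a worthwhile, inexpensive improvement rather than a flaw that invalidates the study.

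**What to change.** 1. In Sampling Frame, replace the statement that representativeness is ensured with one that is conditional on response. State how many students are invited per school and what happens after a school or student declines.
2. Report participation rates for schools and students.
3. In Statistical Analysis, post-stratify the prevalence to enrolment by region, grade and sex, with the region-only estimate beside it. Four regions × five grades × two sexes make 40 cells, or 740/40 = 18.5 students on average, so calibrate to the margins if cells are sparse. The protocol says student numbers by school are published; confirm that they can be had by grade and sex, from the schools if necessary.
4. Pre-specify a sensitivity analysis that recomputes prevalence over a range of R, for example 0.8 to 1.5. Calibration cannot remove OSA-related selection within cells, so this is the step that shows how far the result depends on it.
5. Optional, if the ethics committee agrees: ask all invited families for sex, grade and one habitual-snoring item with the invitation. Use the answers to compare participants with decliners and in a secondary weighted analysis. Families who never reply are still missed.

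Cost: modest variance inflation from the weights and some analysis time. Item 5 also needs ethics wording, a small addition to the invitation paperwork and handling of the returned forms. The documents do not describe that paperwork, so its exact cost cannot be stated. Participation data should be recorded from the first school, since they are hard to recover later.
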